4.2.2. Main analytical approach

The analysis for the primary PK endpoints will be performed for the PK Population.

Pharmacokinetic analysis will be performed to compare the relative bioavailability of a single subcutaneous dose of 100 mg depemokimab administered via an autoinjector compared to a single subcutaneous dose of 100 mg depemokimab administered via SSD.

Based on the individual concentration-time data the following primary plasma PK parameters will be estimated:

C_{\max} and AUC (0- ∞) and AUC(0,t)

Analysis will be performed on the natural logarithms of AUC(0- ∞) and C_{\max} using a fixed-effects analysis of covariance model, with treatment and injection site as categorical covariates, and baseline weight as a continuous covariate fitted on the log scale. Effects will be estimated, and 90% CIs will be constructed for the following treatment comparisons:

Treatment B (Autoinjector) versus Treatment A (SSD)

Point estimates and 90% CIs for treatment differences on the log scale derived from the model will be exponentiated to obtain estimates for geometric mean ratios and CIs on the original scale.

A table will also be produced for the primary ANCOVA analysis of Derived Plasma Depemokimab Pharmacokinetic Parameters { C_{\max} , AUC(0- ∞), AUC(0,t) } by Treatment

to present the CV, R-Square/ Partial Eta-Square, of the model. The Estimates, Standard Error, Precision, of the estimates will also be presented.

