	
from the analyses related to AUC(0-inf) and no missing data imputation will be performed.
 
For participants that withdraw prior to Week 4, or no PK concentrations are available until Week 4, it is anticipated that it will not be possible to derive a reliable value for the PK parameter C_{max}. The participant will be excluded from the analyses related to C_{max} and no missing data imputation will be performed.
 
Rationale for Estimand: Use of prohibited medications is not expected to impact the PK of depemokimab.

Endpoints	Plasma pharmacokinetic parameters: C_{max} and AUC(0- ∞)
Summary Measure	Ratio of the geometric mean of AI versus SSD for C_{max} and AUC(0-inf).

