4.3.1.2. Derived Plasma Pharmacokinetic Parameters

For each participant pharmacokinetic parameters described in Table below will be determined from GSK214099 plasma concentration-time data, as data permit.

Parameter	Parameter Description
AUC(0-t)	Area under the plasma concentration-time curve from time zero to the time of the last quantifiable concentration (C(t)) will be calculated using the linear trapezoidal rule for each incremental trapezoid and the log trapezoidal rule for each decremental trapezoid.
AUC(0-WeekX)	Area under the plasma concentration-time curve from zero to Week X will be calculated using the linear trapezoidal rule for each incremental trapezoid and the log trapezoidal rule for each decremental trapezoid. Planned parameters are AUC(0-Week18). and AUC(0-Week26).
%AUCex	The percentage of AUC (0-∞) obtained by extrapolation (%AUCex) will be calculated as: $[\text{AUC}(0\text{-inf}) - \text{AUC}(0\text{-t})] / \text{AUC}(0\text{-inf}) \times 100$
t _{max}	Time to reach C _{max} , determined directly from the plasma concentration-time data.
t _{last}	Last time point where the concentration is above the limit of quantification.
CL/F	Apparent clearance $\text{CL/F} = \text{dose} / \text{AUC}(0\text{-inf})$

Parameter	Parameter Description
Vz/F	Apparent volume of distribution following extravascular administration.
λ_z	Terminal phase elimination rate constant. The number of points used to determine λ_z will also be reported.
$t_{1/2}$	Apparent terminal phase half-life will be calculated as: $t_{1/2} = \ln 2 / \lambda_z$

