4.4. Exploratory Endpoint(s) Analyses

To assess the pharmacodynamics of a single subcutaneous dose of depemokimab delivered with a safety syringe device or an autoinjector in healthy adult participants, the ratio to baseline of the eosinophil count will be summarized by treatment group with descriptive statistics. In addition, the absolute blood eosinophil count will be summarized by treatment group with descriptive statistics. Blood sampling time will be related to the start of dosing. Linear and semi-logarithmic individual plasma concentration-time profiles and mean (\pm SD) and median profiles will be plotted for each treatment.

To assess the pharmacokinetics of a single subcutaneous dose of depemokimab delivered in the upper arm, abdomen, or thigh in healthy adult participants, the measured depemokimab plasma concentration at planned visits and the derived PK parameters C_{max} and $AUC(0-inf)$ along with ($AUC(0-t)$, T_{max} , CL/F , Vz/F , λ_z , $t_{1/2}$, T_{last} and $\%AUC_{ex}$) will be summarized at each nominal time point with descriptive statistics

- by injection site.
- by treatment.
- by treatment group and injection site.
- by treatment group and baseline body weight category.

- by treatment group, injection site and baseline body weight category.

GSK214099 plasma concentration-time data and derived PK parameters C_{max} and AUC(0-inf) along with (AUC(0-t), T_{max} , CL/F, Vz/F, λ_z , t1/2, Tlast and %AUCex) will be listed by injection site, study day, and nominal time.

Summaries, including mean (\pm SD) and median profile plots, will also be produced by treatment group, injection site, treatment group and injection site, treatment group and baseline body weight category (<70kg, 70-<80kg and \geq 80kg), and treatment group, injection site and baseline body weight category. Any subjects randomised in error to the incorrect weight strata will be summarised according to the stratum corresponding to their actual treatment.

Additionally, a fixed-effects analysis of covariance model, with treatment and injection site as categorical covariates, and baseline weight as a continuous covariate fitted on the log scale and including an interaction term between treatment and injection site will be performed for the following PK endpoints:

C_{max} , AUC(0-inf) and AUC(0-t).

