5. SAMPLE SIZE DETERMINATION

A total of approximately 126 (63 per treatment group) participants will be required to complete at least Week 18 of the study.

The primary aim of this study is to estimate the relative bioavailability of the autoinjector compared with the PFS. Therefore, the sample size calculation for this study is based on the number of participants needed to achieve an acceptable level of precision in the estimate of relative bioavailability.

The variability of depemokimab PK parameters (AUC and C_{max}) was informed by the depemokimab FTIH Study 205722 and the mepolizumab Phase 1 Study 204958 and is in line with results reported for monoclonal antibodies against soluble targets delivered subcutaneously.

Between subject variability (CV_b) of 30% was assumed for both AUC(0-inf) and C_{max} . Based on this CV_b , with a sample size of 63 participants per treatment group, the 90% CI for an estimated ratio of autoinjector versus PFS of 1.00 will be (0.92, 1.09).

In addition, assuming a within-subject correlation of 0.8 between AUC and C_{max} , and a true ratio of 1, a sample size of 63 participants will also provide 90% power to observe geometric CI of geometric mean ratio within the bioequivalence range of (0.8, 1.25) for both parameters.

Approximately 140 healthy participants will be enrolled (accounting for drop-out rate of 10% until Week 18) resulting in at least 126 evaluable participants (approximately 63 for each treatment group, 21 per injection anatomical site within each treatment group).

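### SAP 4.2.2 treats AUC(0-t) as a primary parameter without the Week 18 rule given to AUC(0-inf), so early leavers can widen the interval of what should be a supportive comparison

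*SAP*

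**What the plan says.** **Status of AUC(0-t).** Protocol Table 2 and SAP 1.1 name Cmax and AUC(0-inf) as primary and AUC(0-t) as secondary. SAP 4.2.1 defines only the two primary parameters. SAP 4.2.2 then adds AUC(0-t) to its list of primary parameters and states: "A table will also be produced for the primary ANCOVA analysis of Derived Plasma Depemokimab Pharmacokinetic Parameters", with all three in the braces that follow. The model sentence in the same section names only AUC(0-inf) and Cmax, and continues: "Effects will be estimated, and 90% CIs will be constructed for the following treatment comparisons". SAP 4.4 includes AUC(0-t) in the exploratory ANCOVA with the treatment-by-site interaction, and in the treatment-ratio plots attributed to the primary analysis. SAP 4.8, on changes from the protocol, does not mention AUC(0-t).

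**Who is counted.** SAP 1.1 removes a participant who withdraws before Week 18 "from the analyses related to AUC(0-inf) and no missing data imputation will be performed". A parallel rule at Week 4 covers Cmax. No rule covers AUC(0-t), which SAP 4.3.1.2 defines as "Area under the plasma concentration-time curve from time zero to the time of the last quantifiable concentration". One evaluable sample is enough for the PK analysis set (SAP 3), and Protocol 7.3 keeps data collected up to withdrawal.

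**Fixed-horizon areas.** SAP 4.3.1.2 also plans AUC(0-Week18) and AUC(0-Week26). Neither is named in any model.

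**The concern.** AUC(0-t) is the exposure measure most directly shortened by early exit. The plan recognises that early leavers lack usable data for AUC(0-inf) and Cmax, yet it lets them into the AUC(0-t) comparison with whatever area they accumulated. A short area adds a large negative deviation on the log scale that has nothing to do with the device. It inflates the residual variance, and if the two arms happen to lose different numbers it shifts the ratio.

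The resulting ratio would stand in a primary table and plot next to AUC(0-inf), and the two could disagree for reasons of follow-up alone. SAP 4.2.2 also leaves the programmer unsure whether AUC(0-t) is a primary analysis, because its parameter list and table say one thing and its model sentence another. In an open-label trial, settling either matter after seeing the data would look selective.

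**Working it through.** **1. Reproduce the plan's figure.** SAP 5 gives a between-subject CV "of 30% was assumed for both AUC(0-inf) and" Cmax, and: "A total of approximately 126 (63 per treatment group) participants will be required to complete at least Week 18 of the study".
- SD(log) = sqrt(ln(1 + 0.30²)) = 0.2936.
- 90% CI at ratio 1.00 = exp(± 1.645 × 0.2936 × sqrt(2/63)) = 0.918 to 1.090, or 0.917 to 1.091 with t on 124 df. This matches the stated (0.92, 1.09).
- Enrolment: 126/0.9 = 140, so about 14 leave before Week 18.

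**2. Area captured by the last sample.** Half-life is 41 days (Protocol 6.7; Section 4.2 says about 6 weeks), so ke = ln 2/41 = 0.0169 per day. The absorption rate is not in the documents; I assume ka = 0.25 per day and a one-compartment model. The fraction of AUC(0-inf) by time t is

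F(t) = 1 − (ka·e^(−ke·t) − ke·e^(−ka·t))/(ka − ke), with t = study day − 1.

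For Day 29: F(28) = 1 − (0.25 × 0.6229 − 0.0169 × 0.0009)/0.2331 = 0.332. F(182) = 0.951. The ratio is 0.35.

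| Last sample | Area relative to Day 183 |
|---|---|
| Day 8 | 0.06 |
| Day 15 | 0.16 |
| Day 29 | 0.35 |
| Day 57 | 0.61 |
| Day 85 | 0.78 |
| Day 127 (Week 18) | 0.92 |

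Varying Tmax from 5 to 14 days and half-life from 41 to 42 days gives 0.15-0.20 at Day 15, 0.33-0.38 at Day 29 and 0.60-0.63 at Day 57, so the choice of ka matters little.

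**3. Effect on the AUC(0-t) interval.** Let p = 0.10 be the dropout proportion, and let m and s be the mean and SD of the log shortfall among dropouts. Then

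SD² = 0.2936² + p(s² + m²) − (pm)², and 90% CI = exp(± 1.656 × SD × sqrt(2/70)).

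Example (dropout uniform in time from 24 h to Week 18, last scheduled sample): 0.0862 + 0.1 × (1.061² + 1.002²) − 0.100² = 0.289, so SD = 0.54.

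The schedule table as supplied does not show whether a PK sample is taken at the early-discontinuation visit, so both cases were run.

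| Dropout timing (assumed) | Last PK sample | m | s | SD | 90% CI, formula | 90% CI, simulated median |
|---|---|---|---|---|---|---|
| Uniform, 24 h to Week 18 | last scheduled | −1.00 | 1.06 | 0.54 | 0.86-1.16 | 0.87-1.15 |
| Uniform, 24 h to Week 18 | at withdrawal | −0.76 | 0.92 | 0.47 | 0.88-1.14 | 0.88-1.13 |
| Uniform, after Day 8 | last scheduled | −0.83 | 0.70 | 0.44 | 0.88-1.13 | 0.88-1.13 |
| Uniform, after Day 8 | at withdrawal | −0.60 | 0.57 | 0.39 | 0.90-1.11 | 0.90-1.11 |
| Uniform, after Week 4 | last scheduled | −0.55 | 0.33 | 0.35 | 0.91-1.10 | 0.91-1.10 |
| Uniform, after Week 4 | at withdrawal | −0.37 | 0.25 | 0.32 | 0.91-1.10 | 0.91-1.10 |
| All last sampled at Day 85 | Day 85 | −0.25 | 0 | 0.30 | 0.92-1.09 | not run |

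Simulated values are medians over 20,000 trials with a true ratio of 1. The average ratio was 1.00 in every simulated scenario.

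**4. Uneven dropout by chance.** If 10 leave the autoinjector arm and 4 the SSD arm, the expected log ratio shifts by (10 − 4)/70 × m. A true 1.00 becomes exp(−0.086) = 0.92 in the first row and exp(−0.032) = 0.97 for dropout after Week 4 with a sample at withdrawal. With the split reversed, the ratio moves up by the same factor. With 14 leavers among 70 + 70, a split at least this uneven in either direction has probability 0.16 (hypergeometric).

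**5. After the fix.** With 63 Week 18 completers per arm, AUC(0-Week18) returns to 0.917-1.091; it covers about 0.87 of AUC(0-inf). AUC(0-t) under the Week 18 rule gives practically the same interval (about 0.917-1.09 with three participants per arm last sampled at Week 18), because such a participant already has 0.92 of the Day 183 area.

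**The case against.** The strongest reply is that nothing important rests on AUC(0-t). The estimand uses Cmax and AUC(0-inf), each with its own rule. No hypothesis is tested, and the comparison with 0.80-1.25 in Protocol 9.1 follows the intervals for those two parameters. On this view the wording in SAP 4.2.2 is a labelling slip. That stands as far as the primary result goes, and it is why this is not a must-fix. It does not answer the missing rule: followed as written, the plan yields a needlessly imprecise ratio in a table called primary.

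Three stronger readings are tempting, and the documents support none of them.

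- A reader might infer that truncation will overwhelm the device comparison. That depends on when people leave, and the documents give only 10% by Week 18. Participants stay in the clinic to Day 3, so the earliest exits should be few, and after Week 4 the loss is small.
- A reader might infer that the ratio would measure dropout rather than bioavailability. About 126 of 140 participants contribute near-complete areas, and if dropout is unrelated to device the expected ratio is unchanged. The cost is precision and chance imbalance.
- A reader might infer that AUC(0-Week18) is never analysed. SAP 4.3.1.1 promises a general summary and listing of PK parameters, and display details are left to a separate specification. What can be said is that no model names it.

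**Conclusion.** The point holds as a lower-severity correction. SAP 4.2.2 is inconsistent about whether AUC(0-t) is primary, and AUC(0-t) enters the ANCOVAs of 4.2.2 (through its table) and 4.4 without the follow-up rule that both true primary parameters have. Depending on dropout timing, its 90% CI could stay near the planned 0.92-1.09 or widen to about 0.87-1.15. A 10 v 4 split of dropouts against the autoinjector would move a true ratio of 1.00 to about 0.92-0.97.

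These sizes rest on the plan's 30% CV and 10% dropout, the 41-day half-life, the assumed absorption rate and the assumed timing of exits. Timing matters most and is not documented. The textual finding needs none of these assumptions.

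**What to change.** - In SAP 4.2.2, remove AUC(0-t) from the primary parameter list and label its ANCOVA and table supportive. Label the corresponding ratio plot in 4.4 in the same way.
- In SAP 4.2.2 and 4.4, either apply to AUC(0-t) the Week 18 rule already written for AUC(0-inf), or run the supportive ANCOVA on AUC(0-Week18) in Week 18 completers. The first needs one sentence. The second also gives a check on AUC(0-inf) that involves no extrapolation.
- If AUC(0-Week26) is modelled, restrict it to participants with data to Week 26; the Week 18 rule does not ensure that.

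The cost is SAP wording and a small programming change, with no new data. Early leavers are lost from one supportive comparison, as they already are from AUC(0-inf). The change should be made before the data are analysed.

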4.3. Secondary Endpoint(s) Analyses

4.3.1. [Key/Confirmatory] secondary endpoint(s)

4.3.1.1. Definition of [endpoint(s)/estimands]

GSK214099 plasma concentration-time data and PK Parameters will be Summarized and listed by injection site, study day, and nominal time.

Immunogenicity assessment will be done for depemokimab delivered with a safety syringe device SSD or an autoinjector in healthy adult participants.

4.3.1.2. Derived Plasma Pharmacokinetic Parameters

For each participant pharmacokinetic parameters described in Table below will be determined from GSK214099 plasma concentration-time data, as data permit.

Parameter	Parameter Description
AUC(0-t)	Area under the plasma concentration-time curve from time zero to the time of the last quantifiable concentration (C(t)) will be calculated using the linear trapezoidal rule for each incremental trapezoid and the log trapezoidal rule for each decremental trapezoid.
AUC(0-WeekX)	Area under the plasma concentration-time curve from zero to Week X will be calculated using the linear trapezoidal rule for each incremental trapezoid and the log trapezoidal rule for each decremental trapezoid. Planned parameters are AUC(0-Week18). and AUC(0-Week26).
%AUCex	The percentage of AUC (0-∞) obtained by extrapolation (%AUCex) will be calculated as: $[\text{AUC}(0\text{-inf}) - \text{AUC}(0\text{-t})] / \text{AUC}(0\text{-inf}) \times 100$
t _{max}	Time to reach C _{max} , determined directly from the plasma concentration-time data.
t _{last}	Last time point where the concentration is above the limit of quantification.
CL/F	Apparent clearance $\text{CL/F} = \text{dose} / \text{AUC}(0\text{-inf})$

Parameter	Parameter Description
Vz/F	Apparent volume of distribution following extravascular administration.
λ_z	Terminal phase elimination rate constant. The number of points used to determine λ_z will also be reported.
$t_{1/2}$	Apparent terminal phase half-life will be calculated as: $t_{1/2} = \ln 2 / \lambda_z$

4.3.1.3. Main analytical approach

The analysis for the secondary PK endpoints will be performed for the PK Population.

Summary statistics for C_{max} and AUC (0- ∞), AUC(0-t), T_{max} , CL/F, Vz/F, λ_z , $t_{1/2}$, Tlast and %AUCex (arithmetic mean, geometric mean, median, 95% CI [arithmetic and geometric], standard deviation [arithmetic and on ln-scale], minimum, maximum, and geometric coefficient of variation [CV]). For T_{max} and Tlast, median, minimum, and maximum only will be reported for each treatment group.

4.3.1.4. Immunogenicity Analyses

The immunogenicity assessment for anti-depemokimab antibodies will utilize a tiered analysis approach: an anti-drug antibody (ADA) binding assay that includes a screening assay, a confirmation assay and a titration assay; and a neutralizing antibody assay (NAb). The binding ADA and NAb results at each available timepoint, including Pre-dose as well as at any time post-baseline, will be summarised. Summary statistics for the titre result will also be presented by visit and treatment.

The binding ADA results at each visit will be categorised as a negative or positive, with sub-categories for transient positive (defined as a single confirmatory positive immunogenic response that does not occur at the final study assessment) or persistent positive (defined as a confirmatory positive immunogenic response for at least 2 consecutive assessments or a single result at the final study assessment), and available titre values. If a sample confirms positive, that participants is positive for ADA. Once a sample is characterized as negative, there will be no additional results for that sample. In addition, the highest post-baseline binding ADA confirmatory result obtained for a subject will be summarised. Subjects with both positive and negative results will be

identified in the positive category. Summary statistics for highest titer result will also be presented (including min, median and max).

A summary of adverse events by highest post-baseline binding ADA result will be produced.

A summary of positive confirmation binding ADA assay results in the subset of subjects who did not have a positive confirmation binding ADA result prior to the dosing of study treatment will also be presented.

A summary of neutralizing antibody assay results will summarise the neutralizing antibody assay results for participants with a positive binding antibody confirmatory assay result. Neutralising antibody assay results will be categorised as positive or negative. It will also summarise the highest postbaseline neutralizing antibody assay result obtained.

Immunogenicity Analysis- Adjusted Geometric Mean (95% CI) Ratio to Baseline Blood Eosinophils ($10^9/L$) by Visit and Geometric Mean (95% CI) of Blood Eosinophils ($10^9/L$) by Visit will be produced.

Scatter Plot of Individual Blood Eosinophil-Time Data by Highest Post-Baseline Binding Antibody Result will be produced.

Immunogenicity data will be listed for participants with at least one positive screening binding assay result.

4.4. Exploratory Endpoint(s) Analyses

To assess the pharmacodynamics of a single subcutaneous dose of depemokimab delivered with a safety syringe device or an autoinjector in healthy adult participants, the ratio to baseline of the eosinophil count will be summarized by treatment group with descriptive statistics. In addition, the absolute blood eosinophil count will be summarized by treatment group with descriptive statistics. Blood sampling time will be related to the start of dosing. Linear and semi-logarithmic individual plasma concentration-time profiles and mean (\pm SD) and median profiles will be plotted for each treatment.

To assess the pharmacokinetics of a single subcutaneous dose of depemokimab delivered in the upper arm, abdomen, or thigh in healthy adult participants, the measured depemokimab plasma concentration at planned visits and the derived PK parameters C_{max} and $AUC(0-inf)$ along with ($AUC(0-t)$, T_{max} , CL/F , Vz/F , λ_z , $t_{1/2}$, T_{last} and $\%AUC_{ex}$) will be summarized at each nominal time point with descriptive statistics

- by injection site.
- by treatment.
- by treatment group and injection site.
- by treatment group and baseline body weight category.

- by treatment group, injection site and baseline body weight category.

GSK214099 plasma concentration-time data and derived PK parameters C_{max} and AUC(0-inf) along with (AUC(0-t), T_{max} , CL/F, Vz/F, λ_z , t1/2, Tlast and %AUCex) will be listed by injection site, study day, and nominal time.

Summaries, including mean (\pm SD) and median profile plots, will also be produced by treatment group, injection site, treatment group and injection site, treatment group and baseline body weight category (<70kg, 70-<80kg and \geq 80kg), and treatment group, injection site and baseline body weight category. Any subjects randomised in error to the incorrect weight strata will be summarised according to the stratum corresponding to their actual treatment.

Additionally, a fixed-effects analysis of covariance model, with treatment and injection site as categorical covariates, and baseline weight as a continuous covariate fitted on the log scale and including an interaction term between treatment and injection site will be performed for the following PK endpoints:

C_{max} , AUC(0-inf) and AUC(0-t).

A table will also be produced for the exploratory ANCOVA analysis of Derived Plasma Depemokimab Pharmacokinetic Parameters { C_{max} , AUC(0-inf), AUC(0,t) } by Treatment to present the CV, R_Square/ Partial Eta-Square, of the model. The Estimates, Standard Error, Precision, of the estimates will also be presented.

Plots for Individual Subject (+Geometric Mean and 95% CI) Derived Plasma Depemokimab PK Parameters C_{max} , AUC(0-inf), AUC(0,t) by treatment, by treatment and injection site, by Treatment and Baseline Body weight Category.

Plots for Adjusted Geometric Means and Treatment Ratios (90% CI) for Primary Analysis of Derived Plasma Depemokimab PK Parameter C_{max} , AUC(0-inf), AUC(0,t) will also be produced.

